6.3 Participant Enrollment and Follow-Up

Medicine retail outlets will be eligible if they regularly stock and sell regulatory approved artemether-lumefantrine (AL) and are licensed medicine outlets. From this roster of all eligible outlets, 48 will be randomly selected (8 additional above the required sample size). Of those retail outlets, 40 outlets will be randomly selected for training and enrollment in the study and will be randomized to one of the 4 study arms in a 1:1:1:1 ratio. The remaining 8 outlets will be alternates in the event that any of the initial outlets drop out of the intervention. The alternate

outlets will also be randomized equally across the 4 study arms (2 alternates per arm per site), but they will not undergo training unless they are needed for replacement.

We will retain these enrolled outlets through effective supportive supervision and communication between providers at participating outlets and study staff. All outlets will receive thorough, in-person training on using the mobile reporting tool, conducting RDTs and overall study procedures. They will also receive extra support during the start of the intervention and burn in period (3 months), including an initial stock of RDTs provided by the study at no cost. At least once per month, the PI, Project Manager, and/or Field Coordinator will visit each outlet in person to answer questions, check RDT stock and testing performance, and identify and address any problems. Providers will also receive phone calls from the Field Coordinator and Project Manager between in-person visits and will themselves be provided with phone numbers and encouraged to call the study staff with any questions or concerns. Additionally, outlets will be reimbursed promptly to ensure participation in the study presents no financial strain.

In our previous work, we have had excellent retention of outlets in research activities and therefore have no reason to expect attrition of clusters. However, should one of the outlets selected choose to leave the study within the first 6 months of the intervention, the outlet will be replaced by one of the alternate outlets assigned to the same arm. If any outlet chooses to leave the study after the first 6 months of the intervention, they will not be replaced because, after joining the intervention at such a late stage, a newly added outlet is not likely to be comparable to that of all other participating outlets. Changes in the clusters (dropped and/or replaced) will be accounted for in the analysis.

Our sample size estimates correspond to a total of 6800 exit interviews with clients. Since not everyone interviewed will have purchased an ACT, our estimates account for the fact that only a subset will enter into our analysis for the primary outcome.

6.4 Analysis Plan

We will analyze client-level outcomes by fitting a modified Poisson regression model [30, 31] with log link to estimate risk ratios (RRs) and identity link to estimate risk differences. Such an approach assumes a Poisson distribution for the binary outcome and then 'fixes' the estimated standard errors to correct for model misspecification.

To account for clustering by outlet we will use a generalized estimating equations (GEE) [32, 33] approach with exchangeable working covariance matrix and robust standard errors (to correct for model misspecification due to specifying a Poisson distribution). The outcome will be regressed on three binary indicators for each of the treatment arms 1-3, with treatment arm 4 (the combined interventions) serving as the reference group. The model will also include a vector of potential confounder variables (e.g., age, gender, education, household distance to closest health facility, study quarter) to account for possible imbalances between study arms. All analyses will be based on the intention-to-treat principle whereby all clients will be included in the analysis irrespective of whether they complied with the intervention in the outlet at which

they sought care (e.g. even if they did not use the ACT subsidy if they tested positive in an outlet in Arms 3 and 4 that received the client-directed intervention).

Given that the literature indicates that when there are fewer than 40 clusters in a cRCT, small sample correction methods should be used to ensure that standard error estimates are correctly estimated when using GEE to analyze binary outcomes, and given that the size of the cRCTs in each country are close to this cut-off, we plan to adopt the use of the Kauerman-Carroll correction to avoid any possible problems [34, 35]. We will compare secondary outcomes using the same modeling approach.

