6.2 Sample Size Considerations

Our primary comparison of interest is the effect on targeting of ACTs of offering a combination of outlet incentives for testing (provider-directed intervention), and ACT subsidies for malaria test-positive clients (client-directed intervention) relative to a control arm where outlets are able to offer malaria testing but neither the provider nor the client receives any extrinsic incentive to test (Arm 4 versus Arm 1). In order to evaluate whether the client-directed intervention and the provider-directed intervention do, in fact, have a synergistic effect on the outcome, we also have two secondary comparisons of interest: (1) the combined provider- and client-directed interventions relative to the provider-directed intervention alone (Arm 4 versus Arm 2) and (2) the combined provider- and client- directed interventions relative to the client-directed intervention alone (Arm 4 versus Arm 3).

We calculated power based on a cluster randomized two-sample two-tailed t-test for the comparison of two proportions using standard formulae [27]. We assumed 40 clusters (outlets) would be available to be enrolled based on information about the number of registered pharmacies in the study area. We calculated power for differences in our primary outcome for each of the three comparisons of interest noted above. To ensure that our overall two-tailed Type I error (alpha) is 5%, we fixed the alpha level at 1.667% (i.e. 5%/3) for each of the 3 comparisons of interest, using the conservative Bonferroni correction [28]. We estimated the intra-class correlation coefficients (ICCs) for the primary outcome to be 0.009 in Kenya.

Table 2: Assumptions in Kenya and Nigeria for sample size calculation for Aim 2

	Expected Percentage of ACTs taken by Clients Testing Positive for Malaria		Power (# of exit interviews per arm)		Our primary outcome—the proportion of ACTs that are taken by malaria test-positive clients—is a combination of the proportion of individuals who get tested for malaria and the proportion of tested individuals who treat
	Kenya	Nigeria	Kenya (1700)	Nigeria (2040)	
Arm 1: Control Arm (RDT only, no incentives)	12%	15%	>99%	>99%	
Arm 2: Provider-Directed Intervention (Shopkeeper incentives for malaria testing)	14%	17%	>99%	>99%	
Arm 3: Client-Directed Intervention (ACT subsidy to client conditional on positive test)	19%	26%	91%	89%	
Arm 4: Combined Provider- and Client-Directed Interventions	35%	40%	Ref. Group	Ref. Group	

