according to the test result. We anticipate that 12% of ACTs will be purchased by clients with a positive test in the control arm (with 88% of ACTs purchased by those without a test or with a negative test). Moreover, we hypothesize that both the provider-directed intervention, and the client directed intervention on their own will only increase testing marginally (on the order of ~5 percentage points), but that among those who do test, the client-directed intervention alone will substantially increase the proportion of malaria-positive individuals who take an ACT [29]. As a result, we expect that the provider-directed intervention (Arm 2) will have only a small effect on ACT targeting, that the client-directed intervention (Arm 3) will have a somewhat larger effect, but that the largest effect will come from combining the two interventions (Arm 4) (i.e., we assume a statistical interaction). With a sample of 170 exit interviews per outlet (40 outlets in Kenya), we will have >90% power to detect a minimum difference between Arms 1 and 4 in the primary outcome of 23 percentage points. We will also have >89% power to detect a minimum difference of 16 percentage points for the main secondary comparison of interest (testing uptake).

Due to the nature of the interventions, it is not possible to blind participants and the implementation team to the allocation received. Data collectors will be blinded throughout collection and study statisticians will be blinded during the analysis phase.

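### With covariates in the model, the identity-link Poisson fit in Section 6.4 gives the risk difference only if covariate effects are null or additive, and the plan has no fallback if it fails to fit

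*Combined protocol and SAP*

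**What the plan says.** Section 6.4 (Analysis Plan) analyses client-level binary outcomes by modified Poisson regression, with "log link to estimate risk ratios (RRs) and identity link to estimate risk differences". The Poisson distribution is acknowledged to be wrong for a binary outcome. The stated remedy is that the method "then 'fixes' the estimated standard errors to correct for model misspecification". Clustering is handled by a GEE "approach with exchangeable working covariance matrix and robust standard errors", with a Kauermann-Carroll small-sample correction.

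Arms 1 to 3 enter as three indicators in one model, with Arm 4 as reference. Covariates are added: "The model will also include a vector of potential confounder variables (e.g., age, gender, education, household distance to closest health facility, study quarter" and so on, given as examples. Their coding and the final list are not stated. For the other outcomes, "We will compare secondary outcomes using the same modeling approach".

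Section 6.2 states the planned effect on the difference scale. In its words, "We anticipate that 12% of ACTs will be purchased by clients with a positive test in the control arm"; Table 2 expects 35% in Arm 4, and the text gives a 23-point difference.

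**The concern.** The remedies in Section 6.4 act on the variance. None acts on the quantity to which the point estimate converges. For the log-link Poisson model this is harmless, because the log is the canonical link and the fit reproduces each arm's observed mean. The identity link is not canonical for the Poisson. Once covariates are in the model, the fit no longer reproduces the arm means, so randomisation and covariate balance do not protect the arm coefficient.

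The same covariates are planned on both scales. If arm and covariates both matter, a main-effects model cannot be correct on the log and the identity scale at once. If the plan's log-link model is right, its covariate effects are multiplicative, hence not additive, and its risk-difference model is misspecified.

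At stake is one of the two planned effect scales, for primary and secondary outcomes, and it is the scale on which the design effect is expressed. A second issue is practical. Fitted risks must stay positive, which is hard with additive covariate terms around a 12% risk, and the plan does not say what is reported if the fit fails.

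**Working it through.** **Inputs from Section 6.2 (Kenya).** Risks of 12%, 14%, 19% and 35% in Arms 1 to 4; two-sided alpha 1.667% per comparison; ICC 0.009; 10 outlets per arm.

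**Assumed, because the documents do not give them.** Strength and form of covariate effects; covariate share (40% unless stated); ACT buyers per outlet (25 to 150). Covariates have the same distribution in every arm. The large-sample limits ignore the working correlation.

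**1. The plan's own figures.** 35 − 12 = 23 points (Arm 4 v 1) and 35 − 19 = 16 points (Arm 4 v 3). Power for 23 points is reproducible. With m = 20 buyers per outlet the design effect is 1 + 19 × 0.009 = 1.171, and the effective n per arm is 200/1.171 = 170.8. The SE is √[(0.12×0.88 + 0.35×0.65)/170.8] = 0.0442, and 0.23/0.0442 = 5.2 against a critical value of 2.39. Power is above 99%, as in Table 2.

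**2. Estimating equations.**
- Poisson, identity link: Σ x(y − μ)/μ = 0. Within each arm the mean of y/μ equals 1.
- Poisson, log link, and Gaussian, identity link: Σ x(y − μ) = 0. Within each arm the mean fitted risk equals the observed proportion.

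**3. One case in full.** The covariate is held by 40% of clients with risk ratio 2 in every arm. Arm 1 risks are 0.12/1.4 = 8.57% and 17.14%. Arm 4 risks are 0.35/1.4 = 25% and 50%. The stratum differences are 16.43 and 32.86 points, and 0.6 × 16.43 + 0.4 × 32.86 = 23.0.

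The four-arm identity-link Poisson fit gives 7.8% and 20.2% in Arm 1, and 29.0% and 41.4% in Arm 4. Check for Arm 1: 0.6 × 8.57/7.78 + 0.4 × 17.14/20.22 = 1.00, as the equation requires. The mean fitted risks are 0.6 × 7.8 + 0.4 × 20.2 = 12.8% (observed 12%) and 0.6 × 29.0 + 0.4 × 41.4 = 34.0% (observed 35%). The coefficient is 29.0 − 7.8 = 21.2 points, not 23.0.

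**4. Four-arm limits, multiplicative covariate, 40% share (points).**

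| Covariate RR | 1 | 1.25 | 1.5 | 2 | 3 | 4 |
|---|---|---|---|---|---|---|
| Arm 4 v 1 (true 23.0) | 23.0 | 22.8 | 22.4 | 21.2 | 18.8 | 16.7 |
| Arm 4 v 3 (true 16.0) | 16.0 | 15.9 | 15.7 | 15.1 | 13.8 | 12.5 |

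**5. Other forms, Arm 4 v 1.**
- Logistic covariate effect, OR 1.5/2/3/4: 22.7/22.2/21.2/20.3.
- Additive effect: exactly 23.0.
- Larger difference in the low-risk stratum (50/50 covariate; Arm 1 risks 6% and 18%, Arm 4 risks 35% and 35%): 24.1, so the bias is upward.

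**6. Fitting.** Simulated trials with 40 outlets, ICC 0.009, several categorical covariates and plain Fisher scoring; 100 per setting, so indicative only. Share failing to fit:

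| Covariate effect (range of control risk) | 25 buyers per outlet | 85 | 150 |
|---|---|---|---|
| None (12%) | 63% | 0% | 0% |
| Weak multiplicative (7.8–18.9%) | 68% | 5% | 1% |
| Moderate multiplicative (4.9–29.0%) | 97% | 91% | 89% |
| Moderate logistic (5.4–25.1%) | 88% | 53% | 45% |

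Step-halving reduced the moderate multiplicative row to 89%, 62% and 51%. With age and a skewed distance entered linearly, failure was 53% to 100% (40 trials per setting). With a single binary covariate, 31 buyers per outlet and sensible starting values, there were no failures in 100 trials at each RR of 1.25, 1.5, 2 and 3.

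**7. The alternative.** The identity link with constant (Gaussian) working variance returned 23.0 and 16.0 in every case of steps 4 and 5 in which it was fitted. In the simulations its mean stayed within 0.2 points of the unadjusted difference. It has no positivity constraint.

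**The case against.** The strongest reply is that the key input is missing. The documents report no association between any covariate and the outcome, and they name covariates only as examples, to deal with chance imbalance. Nothing in them suggests that age, gender, education, distance or quarter triples or quadruples the outcome. At RR 1.25 the loss is 0.2 points. The risk ratio, which is sound, is reported alongside. All of this stands. It limits the size and the priority of the point, but not the mechanism.

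A reader might also infer more than the documents support:

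- **That the model never estimates the risk difference, or always shrinks it.** With null or additive covariate effects the limit is exact, and the bias can be upward.
- **That the shortfall is larger than tabulated.** Separate two-arm fits under the same assumptions give 22.3/21.0/18.2/15.8 (Arm 4 v 1) and 15.4/14.4/12.3/10.6 (Arm 4 v 3) for RR 1.5/2/3/4. Section 6.4 fits the four arms jointly, so these do not describe the planned model.
- **That power is materially lost.** The weighting also reduces the standard error. With an assumed 31 buyers per outlet and a normal approximation, Arm 4 v 3 power is 94.4% at RR 2 and 92.8% at RR 3 (Gaussian fit: 96.0% and 97.0%), still above the 91% in Table 2. Arm 4 v 1 stays above 99% even at RR 4. No power claim is made here.
- **That the model will usually fail to fit.** Failure ran from 0% to 100% depending on buyers per outlet, covariate strength and coding, none of which the documents state.

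**Conclusion.** The point holds conditionally. As specified, the adjusted risk difference equals the difference in the outcome proportion only if covariate effects are null or additive across arms. Covariate balance does not rescue it, and neither do the planned standard-error corrections. The plan's own log-link model implies the non-additive case.

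Under the assumptions of step 4, the Arm 4 v 1 shortfall is 0.2 to 0.6 points for covariate RR 1.25 to 1.5, 1.8 at RR 2, and 4.2 to 6.3 at RR 3 to 4. For Arm 4 v 3 it is 0.1 to 0.3, 0.9, and 2.2 to 3.5. The upper end needs strong predictors that the documents do not suggest. Fit failure is a real possibility at a 12% control risk, but its frequency cannot be set from the documents. Without a stated fallback, the risk-difference model could end up being chosen after a failure is seen.

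Risk ratios and unadjusted risk differences are not affected. Priority: should-fix.

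**What to change.** In Section 6.4:

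1. Keep the log-link modified Poisson GEE for risk ratios.
2. Name the marginal risk difference between arms as the target on the difference scale.
3. Estimate it by one pre-specified method, for primary and secondary outcomes: either (a) an identity-link GEE with Gaussian (constant) working variance, exchangeable correlation and Kauermann-Carroll standard errors; or (b) standardisation from the log-link fit, that is, the mean predicted risk with every client set to each arm in turn, with a delta-method standard error from the Kauermann-Carroll covariance matrix.
4. State the covariate list and coding, and what is reported if the chosen fit does not converge. The unadjusted risk difference is one candidate.

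The cost is SAP wording. Data collection, sample size, clustering method and small-sample correction stay as they are.

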6 STATISTICAL CONSIDERATIONS

6.1 Study Outcome Measures

The primary outcome measure is the proportion of all ACTs that are sold to individuals with a positive malaria diagnostic test defined as anyone who is tested at the outlet and receives a positive test result or is referred from a health facility with a documented positive test result.

Among secondary outcomes, behavior will be measured for individuals who were tested at the outlet. Untested clients are those who chose not to be tested and did not come with a test result from another facility. The major secondary outcome is the proportion of suspected malaria cases that are tested. This outcome will allow us to determine whether the conditional subsidy can drive demand for testing. Note that “untested people” here refers specifically to individuals that present at the shop without a referral but decline to be tested

people who were tested with an RDT

people who were tested with an RDT + # untested people who purchased an antimalarial

Other secondary outcomes will measure 1) adherence to the RDT result among all those tested at the outlet, 2) proportion of all suspected malaria cases that are managed appropriately (tested for malaria, and use ACT following a positive test or do not purchase an ACT after a negative test), and 3) ACT use by untested clients.

- Secondary outcome 2: Adherence to the RDT result among all those tested in the shop

people who tested positive and purchased ACT + # people tested negative and did not purchase any AM
people who were tested with an RDT

For those who are negative, if they buy any antimalarial (AM), including monotherapies and older therapies, they are not adhering to test result.

- Secondary outcome 3: Proportion of all suspected malaria cases that are managed appropriately in the shop

people who tested positive and purchased ACT + # people tested negative and did not purchase any AM
people who were tested with an RDT + # untested people who purchased an antimalarial

“Untested people” here refers specifically to individuals that present at the shop without a referral but decline to be tested

- Secondary outcome 4: ACT use among untested clients

people who were not tested in the shop and purchased an ACT
people who were not tested in the shop, did not have documentation of test and purchased any AM

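### Adherence (outcome 2) and ACT use in untested clients (outcome 4) compare groups selected after randomisation, and section 6.4 does not recognise this

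*Combined protocol and SAP*

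**What the plan says.** Section 6.4 (Analysis Plan) sets the principle: "All analyses will be based on the intention-to-treat principle whereby all clients will be included in the analysis irrespective of whether they complied". The sentence goes on to say that compliance means compliance with the outlet's intervention, and gives the example of a test-positive client who does not use the subsidy. The same section then says "We will compare secondary outcomes using the same modeling approach", so secondary outcomes get the same GEE arm contrasts under the same principle.

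Section 6.1 (Study Outcome Measures) prints narrower denominators:

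- Outcome 2 is headed "Secondary outcome 2: Adherence to the RDT result among all those tested in the shop".
- The denominator of outcome 4 is "people who were not tested in the shop, did not have documentation of test and purchased any AM".
- The denominators of testing uptake and of outcome 3 are people tested with an RDT plus untested people who bought an antimalarial.

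For the primary outcome, section 6.3 says that "only a subset will enter into our analysis for the primary outcome".

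Testing is itself an outcome. Of testing uptake, section 6.1 says "This outcome will allow us to determine whether the conditional subsidy can drive demand for testing". Section 6.2 expects that each single intervention "will only increase testing marginally (on the order of ~5 percentage points"), and section 1.1 hypothesises synergy on testing when the two are combined.

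**The concern.** Randomisation makes the arms comparable for the clients who come to the outlets. It does not make the tested clients in Arm 4 comparable with the tested clients in Arm 1. In Arm 1 they bought a test with no added inducement. In Arm 4 they also include clients drawn in by the free ACT or by a provider who is paid to test. If these added clients would act differently on a result, or test positive at a different rate, outcome 2 differs between arms even when no arm changes what any client does with a result. A real gain could be hidden in the same way. Outcome 4 has the mirror problem: whoever moves into testing leaves its denominator.

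At stake is what the trial may conclude about adherence. Nothing in section 6.1 or 6.4 says that these contrasts are conditional, and no analysis of selection into testing is planned.

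**Working it through.** The plan gives no figure to reproduce here. The check compares the text of sections 6.1 and 6.4, then asks how large a spurious difference could be. All uptake and adherence rates below are assumptions unless a source is given.

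**1. Who enters each analysis (section 6.1)**

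| Outcome | Denominator | Post-randomisation selection |
|---|---|---|
| Testing uptake | RDT-tested + untested antimalarial buyers | purchase, if untested |
| 2, adherence | RDT-tested | testing |
| 3, appropriate management | RDT-tested + untested antimalarial buyers | purchase, if untested |
| 4, ACT use in untested | untested, undocumented antimalarial buyers | not testing, and purchase |

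None of these is all clients.

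**2. Two-group arithmetic.** Suppose some clients test in any arm and others test only when incentivised, and each group adheres equally in every arm. Then outcome 2 in the incentivised arm = (t1 × a + (t4 − t1) × b) / t4. Here t1 and t4 are testing uptake in the control and incentivised arms, and a and b are adherence in existing and new testers.

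- t1 = 10%, t4 = 15%, a = 80%, b = 60%: (8 + 3)/15 = 73.3%, against 80.0% in control, a gap of −6.7 points.
- t1 = 10%, t4 = 30%, a = 80%, b = 60%: (8 + 12)/30 = 66.7%, a gap of −13.3 points. Meanwhile tested-and-adherent clients rise from 8% to 20% of all suspected cases.
- t1 = 10%, t4 = 30%, a = 50%, b = 80%: (5 + 16)/30 = 70.0%, against 50.0%, a gap of +20.0 points.
- a = b: no gap.

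**3. Outcome 4, same approach.** Testing goes from 10% to 30%, all untested clients buy an antimalarial, and the ACT share is 90% in never-testers and 70% in switchers. Control: (20 × 0.70 + 70 × 0.90)/90 = 85.6%. Incentivised arm: 90.0%. The apparent rise is 4.4 points with no change in anyone's purchasing while untested.

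**4. Case mix by test result.** Section 1.1 reports that, in earlier studies, up to 70% of test-positive clients did not take an ACT and 1–40% of test-negative clients bought one. Take adherence of 30% after a positive and 99% after a negative, and let positivity among the tested go from 25% to 50% (assumed). Outcome 2 goes from 0.25 × 30 + 0.75 × 99 = 81.8% to 0.50 × 30 + 0.50 × 99 = 64.5%. With 60% after a negative it goes from 52.5% to 45.0%. (Outcome 2 counts any antimalarial after a negative, so the earlier figures are only a guide.)

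**5. Graded selection.** Let keenness u be standard normal, P(adherent) = expit(0.8 + b·u) in every arm, with b = 0.5 or 1.0. The tested are the keenest t% by u itself, or by a variable correlated 0.5 with u. Inputs from section 6.2: 170 interviews per outlet, 10 outlets per arm (40/4), ICC 0.009, alpha 5%/3 = 1.667%. Tested per outlet m = 170 × t. Variance per arm = p(1 − p)[1 + (m − 1)·ICC]/(10m), and the test uses t on 18 df.

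| Testing, control v incentivised | Gap over the four scenarios | Rejection at 1.667%, ICC 0.009 |
|---|---|---|
| 10% v 15% | −0.9 to −1.6 points | about 2–3% |
| 10% v 30% | −2.7 to −5.7 points | 4–29% |
| 30% v 60% | −2.5 to −7.6 points | 5% to 64–65% |

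Worst case in full (30% v 60%, b = 1.0, testing sorted perfectly by keenness): 86.7% v 79.1%, with m = 51 and 102. Design effects are 1 + 50 × 0.009 = 1.45 and 1 + 101 × 0.009 = 1.909. SE = √(0.867 × 0.133 × 1.45/510 + 0.791 × 0.209 × 1.909/1020) = 0.025, and 7.6/2.5 = 3.0 SE. The other three 30% v 60% scenarios reject 5%, 15% and 19% of the time. With ICC 0.05 the design effects become 3.5 and 6.05, the SE 0.042, and the worst case rejects 23% of the time.

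**The case against.** The strongest reply is that the section 6.4 sentence, read to its end, is about compliance: clients who ignore the outlet's intervention stay in that outlet's arm. It does not set out to define denominators. Section 6.1 prints every denominator and labels outcome 2 as "Adherence to the RDT result among all those tested in the shop". Conditional outcomes are legitimate, and testing uptake is already the major secondary outcome, so a careful reader will have both figures. The model also adjusts for covariates such as age, gender, education, distance and quarter.

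Most of this stands. No restriction is hidden, and analysis by allocated arm within a subset does not break arm assignment. But disclosing a denominator is not the same as saying that the contrast has lost the protection of randomisation, and the plan never says the latter. The covariates are included for imbalance between arms. They may remove part of the selection, but none of those listed measures willingness to test.

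The size is also open to challenge, fairly. Uptake of 30% v 60% is assumed. The documents give background testing below 10% (section 1.1) and about 5 points more for each single intervention (section 6.2), with no figure for Arm 4. The ICC of 0.009 and the alpha of 1.667% are stated for the primary outcome, not for adherence.

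A reader might infer that the trial abandons intention-to-treat, or that its adherence result will be wrong. The documents support neither: the sentence is loose rather than false in intent, and the bias vanishes if new testers resemble existing ones. Nor does the point overturn the primary outcome. Its denominator, ACT purchasers, also forms after randomisation, but that outcome describes the mix of ACT sales and not how a fixed group of clients responds to a result.

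**Conclusion.** The point holds as a gap in interpretation. Outcomes 2 and 4 are restricted by behaviour that the arms are meant to change. Section 6.4 places them under an all-clients intention-to-treat principle without recognising that their arm contrasts are conditional.

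Neither size nor direction can be known from the documents. With uptake moving only from 10% to 15%, the graded model gives a negligible gap (at most 1.6 points). With 30% to 60% it gives 2.5 to 7.6 points, and a false-positive rate above nominal in all four scenarios at ICC 0.009. The 64–65% figure is the extreme of those four and should not be cited alone. The two-group arithmetic gives larger gaps, up to 20 points in either direction, when new and existing testers differ by 30 points.

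It is tempting to treat outcome 3 as the randomised alternative, because it does not require a test. Section 6.1 does not support that. An untested client who buys no antimalarial is left out, yet the same client is counted once an incentive leads to a test. Testing uptake as defined has the same feature.

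This merits a change before analysis. It concerns how secondary outcomes are read, not the conduct of the trial.

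**What to change.** 1. In section 6.4, state that clients are analysed by their outlet's allocated arm, whatever they did, within the denominator given for each outcome in section 6.1.
2. State that arm contrasts for outcomes 2 and 4 are conditional on behaviour after randomisation and will be reported as descriptive. Show them beside the testing-uptake contrast, with a table by arm of the characteristics and test positivity of tested clients.
3. Add versions of testing uptake and appropriate management whose denominator is all eligible, interviewed, non-referred clients. Exit interview items 3.1 (tested in the shop), 3.3 (result) and 4.1 (medicines obtained, including none) already supply the data.
4. Do not rest a randomised claim about acting on test results on outcome 3 as now defined.

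The cost is a few sentences, one descriptive table and two further analyses, with no new data collection. The downside is that outcome 2 can no longer be reported as an unqualified treatment effect.
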